6.1 Screening Evaluation

Prior to commencement of this project, the surgical team (inclusive of RMO's, registrars and consultants) and anaesthetic team (RMO's, registrars and consultants) will be orientated to the consenting and recruitment process of this project. All patients to undergo a laparotomy at MBH by a general surgeon as either an elective or emergency procedure will be screened contiguously. They will be recruited once they meet inclusion criteria. At the time of consent to laparotomy, patients will be identified by the surgical registrar or consultant and will be recruited into the study if inclusion criteria are met. The "Poster" and "Recruitment Flowchart" will be printed and laminated and made available in every surgical outpatient and anaesthetic outpatient clinic room to serve as a strict guide to the recruitment process. These are attached. The investigators expect the majority of recruitment to occur in the outpatient setting. The "patient information sheet and consent forms" will be made readily available in the surgical department (ward, outpatient department and acute surgical unit). In regards to emergency surgery and recruitment, if it is deemed patient autonomy is compromised or if due to time constraints their specific concerns are not able to be addressed they will not be recruited in this study. If they meet exclusion criteria the 'Excluded patient data collection tool' is to be completed. If they do not meet exclusion criteria information about the study will be given to the patient and they will be asked to consent for potential enrolment as guided by the patient information sheet (as attached). A copy of the patient consent and recruitment agreement will be kept with the patient's consent to laparotomy. The investigators will enter patient information into a password secured database.

6.2 Study Procedures

6.2.1 Baseline (Day 0)

Data collection tool 'Patient Information' and 'Procedure' filled out by surgical registrar at the end of the procedure (Attached)

6.2.2 Day 1,2,3

Data collection will begin with documenting intraoperative analgesia & anaesthesia requirements. Subsequently data will be collected on the premise of the VAS 12 hours post-operatively (at rest & at coughing) by the Surgical/Anaesthetic Registrar or Consultant. On the surgical ward round the registrar or consultant will ask whether the patient has opened bowel or passed flatus. All data will be recorded on the data collection tool, which will be placed in the patient's chart. The morphine equivalent analgesia can be, but does not have to be filled in. This can be retrospectively analysed for the patient med chart, chart notes, and anaesthetic pain round by the investigators. The investigators will be directly involved in reviewing each patient recruited in this study.

At any stage any complications can be written at the bottom of the Data collection tool.

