All enrolled patient will be randomised into two even arms via random allocation sequence in numbered envelopes. A third party doctor using computer randomisation will conduct the randomisation prior to commencement of the project. The allocation will be revealed prior to closure of the abdomen where the patient will either receive a surgically placed pre-peritoneal catheter or an ultrasound guided rectus sheath catheter inserted by the anaesthetic team prior to waking up from the general anaesthetic.

These catheters will then be intermittently infused with local anaesthetic over the next 72 hours via a pump. Over this time the patients' opiate analgesic requirement and the visual analogue scale (VAS) will be monitored daily. The surgical team and the anaesthetic pain team will review the patients daily for the above and monitor for adverse effects from the procedure/local anaesthetic.

Eligibility Criteria (Inclusion and Exclusion)

Inclusion: All adult general surgical patients undergoing a midline laparotomy at Mackay base hospital

Exclusion Criteria:

- Local Anaesthetic allergy
- Catheter plastic allergy
- Multiple operations as defined as alteration of anatomy of the abdominal wall, preventing placement of catheters.
- Chronic abdominal pain as defined as abdominal pain with opiate use for > 12 weeks
- Abdomen left open
- Patient under 18 years of age
- Pregnant
- Inability of surgical/anaesthetic staff to perform procedure
- Patients with altered cognition (dementia or delirium) and therefore unable to respond to

VAS.

- Patients intubated & therefore unable to communicate

Sample Size Determination:

Calculation of the sample size was performed by using the primary endpoint of 72-hour total morphine usage post laparotomy. In a similar previous study, the total dose of administered morphine was 62mg with a standard deviation of 16mg.⁴ It was decided that a difference of 20% (12mg) would be considered clinically relevant, similar to this previous study.

Assuming $\alpha = 0.05$ and $\beta = 0.15$ (a power of 85 per cent), a total of 66 patients (33 patients per group) would be required to find there was no difference between each group¹⁰. Assuming a 10% dropout rate 72 patients need to be recruited (36 patients per group) to make this number.

2 Introduction

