In this study, the catheters will be inserted and secured by either a surgical or anaesthetic consultant. Surgical consultants and anaesthetic consultants will be orientated to the standard specified procedure (as detailed in section 7.4 of this protocol) of placement as led by [name] (Director of Surgery) prior to the commencement of this study.

3 Objectives

Null hypothesis: Surgically placed pre-peritoneal catheters are superior to ultrasound placed rectus sheath catheters at reducing post-operative pain.

The primary endpoint is:

- Total narcotic usage until day three post op. This will be measured in mg of IV Morphine. All other narcotic agents (Oral or IV) will be calculated back to IV Morphine equivalence as per dosage equivalence on MIMs.

Secondary endpoints:

- Time taken for procedure (Minutes)
- Patient blinded VAS scores at rest and coughing (0-10)
- Time till flatus (Days)
- Time till BO (Days)
- Time till discharge (Days)
- Complications
 - o Wound infection
 - o UTI
 - o VTE

4 Study Design

This will be a randomised, patient blinded trial. All enrolled patient will be randomised into 2 even arms – One to receive a surgically placed pre-peritoneal catheter, the other an ultrasound guided rectus sheath catheter inserted by the anaesthetic team prior to waking up from the general anaesthetic. Both will then receive 72 hours of intermittent Ropivacaine 0.2% boluses via these catheters.

Patients will be screened for the study when they are booked up for an emergency or elective procedure which will always or potentially require a midline laparotomy. These patients will then be consented for potential enrolment. Enrolment and allocation will be only revealed when it is sure that the patient does not meet any of the exclusion criteria in theatre prior to closure of the abdomen via randomised numbered envelopes.

These numbered envelopes will be generated prior to the start of the study by a 3rd party doctor. This doctor, who is not involved in the study in any other way, will use a random allocation sequence generated by computer using non-blocking randomisation.

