Over the first 72hours the patients' opiate analgesic requirement, the visual analogue scale (VAS) and potential complications will be monitored daily by the surgical team and recorded on the data collection tool. During this time the anaesthetic team will also review the patient to monitor the local anaesthetic boluses are being administered correctly via the pumps and to look for adverse effects from the

procedure/local anaesthetic as well. After the 72 hours, unless to patient has ongoing pain issues, the surgical team alone will continue to see the patient daily and record any delayed complications until discharge.

This follow up, other than recording on the data collection sheet, is currently routine care for patients post laparotomy with rectus sheath catheters and will not significantly increase workload for the teams involved during the trial period.

5 Study Population

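### Section 6.2.2 makes same-day recording of the primary endpoint optional and lets unmasked investigators rebuild it later; the bedside questions also lack any not-in-theatre rule

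*Protocol*

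**What the plan says.** **Blinding.** Section 4 states the level plainly: "This will be a randomised, patient blinded trial". No section provides a masked outcome assessor or masked data extraction.

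**Who knows the arm.** From the Synopsis (Study Design): "The allocation will be revealed prior to closure of the abdomen". From the end of section 2: "the catheters will be inserted and secured by either a surgical or anaesthetic consultant". Each of the two teams therefore performs one of the techniques under comparison.

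**Who collects the outcomes.** Section 6.2.2 has the 12-hour VAS taken "at rest & at coughing) by the Surgical/Anaesthetic Registrar or Consultant", and the surgical ward-round registrar or consultant asks about flatus and bowels. In section 4, opioid requirement, VAS and complications "will be monitored daily by the surgical team and recorded on the data collection tool".

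**How the primary endpoint is obtained.** Section 6.2.2 makes the morphine-equivalent field optional and continues: "This can be retrospectively analysed for the patient med chart, chart notes, and anaesthetic pain round by the investigators". The Synopsis and section 3 fix the conversion of other opioids to IV morphine by MIMS equivalence.

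**What the investigators see.** Section 6.2.2 has them directly involved in reviewing every recruited patient. Section 12 has three surgical co-authors observe recruitment, allocation and data collection.

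**Later checks.** An independent surgical registrar audits the spreadsheet (section 11). The Principal Investigator analyses the data and an independent statistician then does so (section 14). Section 10.3 allows a suspect or missing result to be left out, with the reason reported. None of these steps is described as done without knowledge of the arm.

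**The concern.** A single-blind design is legitimate when the operators cannot be masked. It does not follow that the endpoint must be assembled by people who know the arm, and the two should be kept apart.

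The primary endpoint is a 72-hour total. If the daily figure is left blank, someone must later decide which chart entries count, what to do when the medication chart, the notes and the pain-round record disagree, and how to treat an illegible or missing entry. Each decision is small, but made with the arm known they can all lean the same way. The stated goal is to show that the surgical technique is more effective, and the surgical team does the daily recording. The arm can also influence how a VAS or bowel question is put, and whether an odd value is kept or dropped under section 10.3. Bias of this kind is not reduced by a larger sample and cannot be removed in the analysis.

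**Working it through.** **Passages side by side**

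| Step | Protocol | Masked to arm? |
|---|---|---|
| Envelope opened | In theatre before closure (Synopsis) | No |
| Catheter inserted | Surgical or anaesthetic consultant (section 2) | No |
| VAS asked | Registrar or consultant of either team (6.2.2) | Not required |
| Flatus, bowels asked | Surgical ward round (6.2.2) | Not required |
| Morphine equivalent entered on the day | Optional (6.2.2) | Not required |
| Morphine total rebuilt | Investigators, three chart sources (6.2.2) | Not required |
| Conversion factor | MIMS (Synopsis, section 3) | Fixed in advance |
| Odd or missing value left out | Discretionary (10.3) | Not required |

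Only the conversion factor is protected by a rule set in advance. Section 4 and the statement in 6.2.2 that "All data will be recorded on the data collection tool, which will be placed in the" patient's chart point to recording at the time, but the one item 6.2.2 exempts is the primary endpoint.

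**The plan's own figure first.** Inputs from the Synopsis and section 10.2: mean 62 mg, SD 16 mg, difference 20% (stated as 12 mg; 0.20 × 62 = 12.4 mg), alpha 0.05, power 85%. Two-sided testing is assumed because the protocol does not say. With a two-sample t-test (noncentral t):

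- 12 mg, 33 per group: power 85.1%, which matches the Synopsis total of 66.
- 12.4 mg, 31 per group: power 85.1%, which matches the section 10.2 total of 62.

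Both totals are reproduced. Masking changes none of these inputs, so the sample size is unaffected.

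**Illustration of what a shift would do.** Suppose there is no true difference and assessment adds a systematic b mg to one arm.

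- Standard error of the difference = SD × √(2/n) = 16 × √(2/33) = 3.94 mg.
- Noncentrality = b / 3.94, with 64 degrees of freedom and critical value 1.998.

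| Assumed shift b | Noncentrality | Chance of P < 0.05 |
|---|---|---|
| 0 mg | 0 | 5.0% |
| 1 mg | 0.25 | 5.7% |
| 3 mg (about 5% of 62) | 0.76 | 11.7% |
| 6 mg (about 10% of 62) | 1.52 | 32.3% |

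The values of b are assumptions. The documents give no estimate, and the table is not evidence that any such shift will occur.

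**The case against.** The best case for the protocol has five parts.

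1. *The trial says it is single blind.* This stands: there is no contradiction, only a weakness in how data collection is arranged.

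2. *The endpoint is less open to judgement than it looks.* A reader might infer that the investigators choose their own conversions. They do not, since MIMS equivalence is fixed and section 6.2.2 names the sources. What stays open is which of three sources prevails and how entries are read.

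3. *The VAS is a blinded patient's own report*, and flatus and bowel opening are yes/no items. This is real protection. It limits a questioner's influence but does not abolish it, and it does nothing for chart extraction. The shared teams are also not shown to be the same individuals: consultants insert, while registrars or consultants ask. Because either team may take the VAS, a consistent lean towards the surgical arm is not established.

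4. *The chart is not shown to disclose the arm.* The Procedure part is "filled out by surgical registrar at the end of the procedure" and the tool is kept in the chart, so a reader might infer that it tells ward staff the allocation. The form is not at hand, and the time-of-procedure items in the schedule table list neither arm nor operator. The inference is not supported.

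5. *Audit and an independent statistician follow.* They help with transcription errors. Neither is stated to be blind to arm, and neither redoes the choice of source entries.

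A further reply is that working on a file without the arm belongs in an analysis plan. That is partly fair. But who extracts the primary endpoint, when and from what is a data-collection rule that section 6.2.2 itself sets.

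**Conclusion.** The point holds in a limited form. The protocol makes same-day recording of the primary endpoint optional and permits, though it does not require, retrospective reconstruction by investigators with no masking stated. It also sets no rule that the person asking about pain and bowel function was not in theatre. The first matters more, because the patient's blinding gives it no protection.

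The size is unknown. Under assumed shifts the false-positive rate would be about 5.7% (1 mg), 12% (3 mg) or 32% (6 mg), with 33 per arm, SD 16 mg and a two-sided 5% test. A small shift does little harm, while one approaching 10% of the expected total would be serious.

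One might go further and say that full masking is almost free because both techniques use the same catheter, securement device and filter. The documents do not support that. The entry point is 5–7 cm lateral in the ultrasound arm and 5 cm in the surgical arm, a transparent dressing is specified in the surgical technique, and no roster is given. Confidence is moderate: the text is clear, but the data forms are not shown and the effect cannot be sized. The change should be made.

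**What to change.** 1. **Section 6.2.2, primary endpoint.** Remove the wording that makes the morphine field optional. Require each opioid's drug, dose, route and time for days 1–3 to be transcribed from the medication chart, named as the single primary source, by a team member who was not in theatre for that patient. Apply the existing MIMS conversion on a file that does not carry the arm.

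2. **Section 10.3, exclusions.** State that any decision to leave out a suspect or missing value is made without the arm.

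3. **Section 6.2.2, VAS and bowel questions.** Have the patient mark the VAS. Otherwise have it, and the flatus and bowel questions, asked by an existing ward-round or pain-round doctor who was not in theatre for that patient, where the roster allows.

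The operation note should keep its record of the technique: staff must watch for technique-related events (section 8.1), so removing it would carry a safety cost.

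**Cost.** Protocol wording, a revised Day 1–3 page, some ward entry time and a rostering constraint. No additional staff should be needed, and neither treatment nor sample size changes. Masking will be imperfect, because chart notes, entry point or dressing may still reveal the arm.

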6.2.1 Chart Follow up

Prior to completely de-identifying the patient, late complications will be assessed 2 months post op via a chart review.

	Procedure	Length of incision (cm)	Midline Incision (full/upper/lower)	Stoma (Y/N)	Anaesthetic used	Time taken for catheter (min)	Morphine equivalent analgesia (mg)	VAS Score at rest	VAS Score on coughing	Passed Flatus (Y/N)	Bowels Opened (Y/N)	Complications
Time of procedure	X	X	X	X	X	X						X
Day 1 post op							X	X	X	X	X	X
Day 2 post op							X	X	X	X	X	X
Day 3 post op							X	X	X	X	X	X
Chart Review							X			X	X	X

Copies of the Data collection sheets are attached

6.3 Study Restrictions

6.3.1 Adverse Events

- Wound infection
- Haematoma
- Local anaesthetic toxicity

7 Investigational product(s)

7.1 Description of Investigational Product(s)

- 16G Portex® Extra length (110mm) Tuohy Needle
- 16G Epidural Catheter (Multiperforated with 3 lateral eyes)
- 16/17G LOCKIT PLUS™ Regional Anaesthesia Catheter Securement Device
- Alaris Products® 0.2µm Line Filters
- Opsite® Flexigrid (10x12cm)
- 20mL Luer-lock Syringe

See Figure 1 for a complete picture of all products used

Figure 1: Equipment used

7.2 Dose Justification

Re: Ropivacaine HCl

TGA approved indications include field block (minor nerve block and infiltration) at a dose as below:

- Initial bolus: 2mg/Kg (For 0.2% (2mg/mL) 1mL/Kg)
- Ongoing infusion of Ropivacaine 0.2%: **10 – 20 mg/hr** (5 – 10 mL/hr) for up to 72 hours.

Study dose:

- 40mL initial infusion of Ropivacaine 0.2% (80mg)
- 20mL Ropivacaine 0.2% (80mg) every 4 hrs (40mg/4hrs = **10mg/hr** = 5mL/hr)

This is the current protocol at MBH. It is also at the lower range of the of the suggested infusion of Ropivacaine as to lower the small risk of local anaesthetic toxicity.

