16.3	Regulatory Authorities.....	23
16.4	Informed Consent	24
16.6	Emergency Contact with Investigators.....	24
16.7	Notification of Primary Care Physician.....	24
16.10	Protocol Amendments	24
16.11	Protocol Compliance	24
16.12	Archives: Retention of Study Records	24
17	References.....	25

ABBREVIATIONS AND DEFINITIONS OF TERMS (examples only – modify as appropriate)

AE	Adverse Event
BMI	Body Mass Index (weight in kg divided by height in m ²)
BO	Bowels Open
CTN	Clinical Trial Notification
ECG	Electrocardiogram
IEC	Independent Ethics Committee
IV	Intravenous
Hr	Hour
MBH	Mackay Base Hospital
NHMRC	National Health and Medical Research Council
PI	Principal Investigator
®	Registered Product
ROP	Ropivacaine
SAE	Serious Adverse Event
SD	Standard Deviation
US	Ultrasound
UTI	Urinary Tract Infection
VAS	Visual analogue scale (Score of 1-10 for pain)
VTE	Venous Thromboembolism

Protocol Number: 1.02 Version 3

Protocol Title: Randomised single blinded trial of surgically placed pre-peritoneal vs ultrasound placed rectus sheath catheters post laparotomy

1 Synopsis

Study Title:

Randomised single blinded trial of surgically placed pre-peritoneal vs ultrasound placed rectus sheath catheters post laparotomy

Protocol Number:

1.02

Indication:

Patient undergoing a laparotomy (Emergency and Elective) under the general surgical team

Study Drugs:

Testing technique, not drugs. Both arms will then receive 20mL 0.2% Ropivacaine infusion through these catheters every 4 hrs for 3 days.

No. Participants:

72 Patients

No. Centres:

1 Centre; Mackay Base Hospital

Study Duration:

Approximately 1 year

Objectives of the Study:

The goal of this project is to prove if surgically placed pre-peritoneal catheters are more effective than ultrasound placed rectus sheath catheters at improving post-operative pain.

Study Endpoints:

The primary endpoint is:

- Total narcotic usage until day 3 post op. This will be measured in mg of IV Morphine. All other narcotic agents (Oral or IV) will be calculated back to IV Morphine equivalence as per dosage equivalence on MIMs.

Secondary endpoints:

- Time taken for procedure (Minutes)
- Patient blinded VAS scores at rest and coughing (0-10)
- Time till flatus (Days)
- Time till BO (Days)
- Time till discharge (Days)
- Complications
 - o Wound infection
 - o UTI
 - o VTE

Study Design:

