In regards to safety of the rectus sheath catheters with continuous LA infusion, no studies have reported any significant complications.⁵ Two small studies have been done looking for specific complications. The first was an observational, descriptive and prospective study of 50 patients which found that there was no increased incidence of wound infection with a rectus sheath catheter than without post laparotomy.⁹ The second study looked at blood levels, signs or symptoms of LA toxicity in 12 patients who had an U/S guided rectus sheath catheter placed.⁸ The protocol of LA used involved a 20mL bolus of 0.5% ROP followed by 10 mL/h of 0.2% ROP infusion. It found that although the total plasma ROP concentrations just exceeded reported neurotoxicity thresholds, the unbound ROP concentration did not reach the toxicity threshold, and nil patients had any signs or symptoms of toxicity.⁹

It is standard practice for the placement of rectus sheath catheters following major abdominal surgery. A surgeon will insert the rectus sheath catheters prior to closure of the laparotomy incision abutting the transversalis fascia in the pre-peritoneal space. Alternatively an anaesthetist will insert the rectus catheters via US guidance into the rectus abdomini muscle. A detailed description of the technique used by both surgeons and anaesthetist in this study is included in section 7.4 of this protocol. Whilst in the literature both techniques of surgically placed pre-peritoneal catheters and US placed rectus sheath catheters have been found to be effective against placebo there have been no head to head trials to see if one is superior.

The only study directly comparing catheter placement was Khorgami et al.⁴ They compared catheter placement in the rectus sheath (intrafascial) to the Subcutaneous (suprafascial) space. In this study it found that the intrafascial rectus sheath catheters were more effective in reducing morphine requirements, visual analogue scale (VAS) scores and time til BS returns than suprafascial catheters.

This study will be similar in nature to the aforementioned study⁴ with the intention of finding whether a surgically placed pre-peritoneal catheter is a quicker, more effective option to the U/S placed

intrafascial rectus catheter. The other potential benefit theorised would be a decrease in visceral pain with a pre peritoneal catheter.

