- 6) The 16G Epidural Catheter is then inserted through the needle to approx. 10-15cm and the needle is withdrawn slowly to ensure the catheter does not move.
- 7) The Catheter is then secured with the Securement Device.
- 8) The catheter connector, followed by the filter is then attached to the distal end of the catheter
- 9) The process is then repeated on the contralateral side.
- 10) 20mL of 0.2% Ropivacaine is infused on each side.
- 11) Once the wall closure has been completed a large transparent dressing is placed over the insertion site.

Figure 3: Surgical placement location (Pre-Peritoneal)

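### The maintenance ropivacaine dose is given as both 80 mg and 40 mg for the same 20 mL, and the protocol never says whether 20 mL is the total or per catheter

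*Protocol*

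**What the plan says.** Protocol section 7.2 fixes the concentration when it quotes the approved bolus: "Initial bolus: 2mg/Kg (For 0.2% (2mg/mL) 1mL/Kg". It quotes an approved continuing infusion of 10 to 20 mg/h, with the volume equivalent "5 – 10 mL/hr) for up to 72 hours".

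The study dose then has two lines. The initial dose is "40mL initial infusion of Ropivacaine 0.2% (80mg". The maintenance dose is "20mL Ropivacaine 0.2% (80mg) every 4 hrs (40mg/4hrs", and the line goes on to equate this with 10 mg/h and 5 mL/h. The section justifies the choice on safety grounds: "It is also at the lower range of the of the suggested infusion of Ropivacaine as to lower the small risk of local anaesthetic toxicity".

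Two other places bear on the volume:

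- Synopsis, Study Drugs: "Both arms will then receive 20mL 0.2% Ropivacaine infusion through these catheters every 4 hrs for 3 days". No mass is given, and no split between the catheters.
- Section 7.4: both techniques are bilateral (step 9 repeats the insertion on the other side). Step 10 of the surgical technique gives the first dose as "20mL of 0.2% Ropivacaine is infused on each side". The ultrasound technique likewise uses 20 mL for each side.

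**The concern.** One line of the dose section assigns two masses, a factor of two apart, to one bolus that is repeated every four hours for three days. If 80 mg were plainly a slip of the pen, the volume would settle the matter. It does not quite do so, because the protocol has already used 20 mL to mean 20 mL per side for the first dose, and that reading of the maintenance dose yields exactly the printed 80 mg.

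The main issue is the safety argument. The claim that the regimen sits at the low end of the quoted range is true under one reading and false under the other. The higher reading also matches the infusion rate of the pharmacokinetic study summarised in section 2: "The protocol of LA used involved a 20mL bolus of 0.5% ROP followed by 10 mL/h of 0.2% ROP infusion". Section 2 reports that total plasma concentrations in that study just passed the reported neurotoxicity thresholds. It also reports that unbound concentrations did not reach the toxicity threshold and that no patient had signs or symptoms. Section 8.1 classes likely systemic toxicity as a serious adverse event, and section 9.2 makes any such event a reason to discontinue, so the intended rate should be beyond doubt.

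A secondary point is that if staff applied different readings, patients would receive different amounts of local anaesthetic, which could plausibly add variation to opioid use, the primary endpoint.

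**Working it through.** Inputs, all from the protocol: concentration 2 mg/mL (7.2); maintenance volume 20 mL every 4 h (Synopsis, 7.2); initial volume 40 mL (7.2), given as 20 mL per side (7.4); two catheters (7.4, step 9); quoted range 5 to 10 mL/h (7.2); duration 72 h.

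Formulas: mass = volume × concentration; rate = mass ÷ 4 h.

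**Figures that reproduce**

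- Initial dose: 40 mL × 2 mg/mL = 80 mg. Agrees with 7.2 and with 2 × 20 mL in 7.4.
- Quoted range: 5 × 2 = 10 mg/h and 10 × 2 = 20 mg/h. Agrees.
- Maintenance rate: 20 mL × 2 mg/mL = 40 mg; 40 ÷ 4 = 10 mg/h; 20 ÷ 4 = 5 mL/h. Agrees with the second half of the line.

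**Figure that does not reproduce**

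- The 80 mg label on 20 mL: 20 × 2 = 40 mg, so the label is 80 ÷ 40 = 2 times the content of the stated volume. It can be recovered only as 2 catheters × 20 mL × 2 mg/mL = 80 mg.

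**The two readings**

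The 72 h totals assume 72 ÷ 4 = 18 maintenance boluses and leave out the 80 mg initial dose.

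| | 20 mL in total | 20 mL per catheter |
|---|---|---|
| Volume per administration | 20 mL | 40 mL |
| Mass per administration | 40 mg | 80 mg |
| Rate | 10 mg/h, 5 mL/h | 20 mg/h, 10 mL/h |
| Per 24 h (6 boluses) | 240 mg | 480 mg |
| Over 72 h (18 boluses) | 720 mg | 1440 mg |
| Place in the quoted range | bottom | top |
| Agrees with the 80 mg label | no | yes |
| Agrees with the stated 40 mg per 4 h, 10 mg/h and 5 mL/h | yes | no |
| Agrees with the lower-range sentence | yes | no |

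Neither column agrees with everything in section 7.2.

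**Comparison with the cited study**

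Its infusion was 10 mL/h × 2 mg/mL = 20 mg/h, the same rate as the right-hand column. Its bolus was 20 mL of 0.5%, that is 20 × 5 = 100 mg against 80 mg here, so only the infusion rates match, not the whole regimens.

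**The case against.** The strongest reply is that the two readings are not evenly supported. The 20 mL volume, the 40 mg per 4 h, the 10 mg/h, the 5 mL/h and the lower-range sentence all fit together, and only the 80 mg label is out of line. The line above ends with the same 80 mg, correctly, so a carry-over is plausible. The synopsis puts a single volume through plural catheters, which reads more naturally as a total, and where the protocol means per side, as in section 7.4, it says so. Section 7.4 covers only the first dose and is internally consistent.

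This is fair as to the weight of the text. It does not remove the contradiction, and no sentence states that the maintenance 20 mL is a total. The appeal in section 7.2 to existing hospital practice does not help, because that practice is not set out in the protocol. The check in section 4 that boluses are being given correctly presupposes one defined dose.

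Two further objections stand in part. Both readings lie within the quoted 10 to 20 mg/h, so nothing here shows that the range would be exceeded. The effect on the primary endpoint is not quantified: both arms follow the same regimen, so mixed readings would add noise with no evident direction, and nothing in the protocol shows that staff would in fact differ. The case for correction rests on the dose and its safety justification, not on the endpoint.

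**Conclusion.** The concern holds: the maintenance line is wrong as written. At the protocol's own 2 mg/mL, 20 mL is 40 mg and cannot also be 80 mg. The discrepancy is a factor of two in each maintenance dose: 10 against 20 mg/h, or 720 against 1440 mg over 72 h if 18 boluses are given. That factor is the gap between two readings, not a predicted dosing error.

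The uncertainty over total or per-catheter volume is also real, although more of the text points to a total. The stated safety rationale survives only under the 10 mg/h reading. This must be corrected because it concerns a repeated drug dose in the section that justifies its safety. No view is taken here on which dose is right.

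**What to change.** Reconcile the Synopsis (Study Drugs) and section 7.2, and check them against section 7.4. For the maintenance dose, state volume per catheter, total volume per administration, total mg per administration and mg/h, with all four agreeing at 2 mg/mL. Label the initial dose in the same way, so that per-side and total volumes cannot be confused. Then re-read the lower-range sentence in section 7.2 against the reconciled rate, and keep or revise it accordingly. The investigators must decide which figure is intended.

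The cost is small: a short correction to the dose line and the synopsis, plus a check that any pump orders or prescriptions used at the site carry the same figures. Section 15.6 exempts only administrative changes such as spelling, so a correction to a stated dose should go through the ethics committee and site governance. Design, sample size and analysis are unaffected.
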